### 7.1.2 Disease Parameters

Measurable disease. Measurable lesions are defined as those that can be accurately measured in at least one dimension (longest diameter in the plane of measurement is to be recorded) with a minimum size of:

- 10mm by CT scan (irrespective of scanner type) for studies with a slice thickness of  $\leq 5$ mm or twice the slice thickness or MRI
- 10mm caliper measurement by clinical exam (lesions which cannot be accurately measured with calipers should be recorded as non-measurable)
- 20mm by chest X-ray (if clearly defined and surrounded by aerated lung)

All tumor measurements must be recorded in millimeters (or decimal fractions of centimeters).

Malignant lymph nodes: To be considered pathologically enlarged and measurable, a lymph node must be  $\geq 15$ mm in short axis when assessed by CT scan (CT scan slice thickness recommended to be no greater than 5 mm). At baseline and in follow-up, only the short axis will be measured and followed.

Note: Tumor lesions that are situated in a previously irradiated area are not considered measurable.

Non-measurable disease. All other lesions (or sites of disease), including small lesions (longest diameter  $< 20$  mm with conventional techniques or  $< 10$  mm using CT scan), are considered non-measurable disease. Bone lesions, leptomeningeal disease, ascites, pleural/pericardial effusions, lymphangitis cutis/pulmonis, inflammatory breast disease, abdominal masses (not followed by CT or MRI), and cystic lesions are all non-measurable.

Target lesions. All measurable lesions up to a maximum of 2 lesions per organ and 5 lesions in total should be identified as **target lesions** and recorded and measured at baseline. Target lesions should be selected on the basis of their size (lesions with the longest diameter), be representative of all involved organ, but in addition should be those that lend themselves to reproducible repeated measurements.

Lymph nodes merit special mention since they are normal anatomical structures which may be visible by imaging even if not involved by tumor. Pathological nodes which are defined as measurable and may be identified as target lesions must meet the criterion of a short axis of  $\geq 15$ mm by CT scan. Only the short axis of these nodes will contribute to the baseline sum. The short axis of the node is the diameter normally used by radiologists to judge if a node is involved by solid tumor. Nodal size is normally reported as two dimensions in the plane in which the image is obtained (for CT scan this is almost always the axial plane; for MRI the plane of acquisition may be axial, sagittal or coronal). The smaller of these

measures is the short axis. For example, an abdominal node which is reported as being 20mm x 30mm has a short axis of 20mm and qualifies as a malignant, measurable node. In this example, 20mm should be recorded as the node measurement. All other pathological nodes (those with short axis  $\geq 10$ mm but  $< 15$  mm) should be considered non-target lesions. Nodes that have a short axis  $< 10$ mm are considered non-pathological and should not be recorded or followed. A sum of the diameters (longest for non-nodal lesions, short axis for nodal lesions) for all target lesions will be calculated and reported as the baseline sum diameters. If lymph nodes are to be included in the sum, then as noted above, only the short axis is added into the sum. The baseline sum diameters will be used as reference to further characterize any objective tumor regression in the measurable dimension of the disease.

Non-target lesions. All other lesions (or sites of disease) including pathological lymph nodes should be identified as non-target lesions and should also be recorded at baseline. Measurements are not required and these lesions should be followed as 'present', 'absent', or in rare cases 'unequivocal progression' (more details to follow). In addition, it is possible to record multiple non-target lesions involving the same organ as a single item on the case record form (e.g. 'multiple enlarged pelvic lymph nodes' or 'multiple liver metastases').

### 7.1.3 Guidelines for Evaluation of Measurable Disease

All measurements should be recorded in metric notation, using calipers if clinically assessed. All baseline evaluations should be performed as close as possible to the treatment start and never more than 4 weeks before the beginning of the treatment.

The same method of assessment and the same technique should be used to characterize each identified and reported lesion at baseline and during follow-up. Imaging based evaluation should always be done rather than clinical examination unless the lesion(s) being followed cannot be imaged but are assessable by clinical exam.

**Clinical lesions:** Clinical lesions will only be considered measurable when they are superficial and  $> 10$ mm diameter as assessed using calipers (e.g. skin nodules). For the case of skin lesions, documentation by color photography including a ruler to estimate the size of the lesion is suggested. As noted above, when lesions can be evaluated by both clinical exam and imaging, imaging evaluation should be undertaken since it is more objective and may also be reviewed at the end of the study.

**Chest X-ray:** Chest CT is preferred over chest X-ray, particularly when progression is an important endpoint, since CT is more sensitive than X-ray, particularly in identifying new lesions. However, lesions on chest X-ray may be considered measurable if they are clearly defined and surrounded by aerated lung.

**CT, MRI:** CT is the best currently available and reproducible method to measure lesions selected for response assessment. This guideline has defined measurability of lesions on CT scan based on the assumption that CT slice thickness is 5mm or less. When CT scans have slice thickness greater than 5 mm, the minimum size for a measurable lesion should be twice the slice thickness. MRI is also acceptable in certain situations (e.g. for body scans).

**Ultrasound:** Ultrasound is not useful in assessment of lesion size and should not be used as a method of measurement. Ultrasound examinations cannot be

reproduced in their entirety for independent review at a later date and, because they are operator dependent, it cannot be guaranteed that the same technique and measurements will be taken from one assessment to the next. If new lesions are identified by ultrasound in the course of the study, confirmation by CT or MRI is advised. If there is concern about radiation exposure at CT, MRI may be used instead of CT in selected instances.

Endoscopy, laparoscopy: The utilization of these techniques for objective tumor evaluation is not advised. However, they can be useful to confirm complete pathological response when biopsies are obtained or to determine relapse in trials where recurrence following complete response or surgical resection is an endpoint.

Cytology, Histology: These techniques can be used to differentiate between PR and CR in rare cases. When effusions are known to be a potential adverse effect of treatment, the cytological confirmation of the neoplastic origin of any effusion that appears or worsens during treatment can be considered if the measurable tumor has met criteria for response or stable disease in order to differentiate between response (or stable disease) and progressive disease.

#### **7.1.4 Response Criteria**

##### **7.1.4.1 Evaluation of Target Lesions**

Complete Response (CR): Disappearance of all target lesions, determined by two separate observations conducted not less than 4 weeks apart. There can be no appearance of new lesions.

Partial Response (PR): At least a 30% decrease in the sum of the longest diameter (LD) of target lesions, taking as reference the baseline sum LD. There can be no appearance of new lesions.

Progressive Disease (PD): At least a 20% increase in the sum of the LD of target lesions, taking as reference the smallest sum LD recorded since the treatment started, or the appearance of one or more new lesions.

Stable Disease (SD): Neither sufficient shrinkage to qualify for PR nor sufficient increase to qualify for PD, taking as reference the smallest sum LD since the treatment started.

##### **7.1.4.2 Evaluation of Non-Target Lesions**

Complete Response (CR): Disappearance of all non-target lesions and normalization of tumor marker level.

Incomplete Response/Stable Disease (SD): Persistence of one or more non-target lesion(s) and/or maintenance of tumor marker level above the normal limits.

Progressive Disease (PD): Appearance of one or more new lesions and/or unequivocal progression of existing non-target lesions.

##### **7.1.4.3 Evaluation of Best Overall Response**

The best overall response is the best response recorded from the start of the treatment until disease progression/recurrence (taking as reference for progressive disease the smallest measurements recorded since the

treatment started). The patient's best response assignment will depend on the achievement of both measurement and confirmation criteria.

Target Lesions	Non-Target Lesions	New Lesions	Overall Response	Best Response for this Category Also Requires:
CR	CR	No	CR	≥4 wks. confirmation
CR	Non-CR/SD	No	PR	≥4 wks. confirmation
PR	Non-PD	No	PR	
SD	Non-PD	No	SD	documented at least once ≥4 wks. from baseline
PD	Any	Yes or No	PD	no prior SD, PR or CR
Any	PD*	Yes or No	PD	
Any	Any	Yes	PD	

* In exceptional circumstances, unequivocal progression in non-target lesions may be accepted as disease progression.
 
Note: Patients with a global deterioration of health status requiring discontinuation of treatment without objective evidence of disease progression at that time should be reported as “symptomatic deterioration”. Every effort should be made to document the objective progression even after discontinuation of treatment.
				

Note: If subjects respond to treatment and are able to have their disease resected, the patient's response will be assessed prior to the surgery.

**7.1.5 Duration of Response**

Duration of overall response: The duration of overall response is measured from the time measurement criteria are met for CR or PR (whichever is first recorded) until the first date that recurrent or progressive disease is objectively documented (taking as reference for progressive disease the smallest measurements recorded since the treatment started).

The duration of overall CR is measured from the time measurement criteria are first met for CR until the first date that recurrent disease is objectively documented.

Duration of stable disease: Stable disease is measured from the start of the treatment until the criteria for progression are met, taking as reference the smallest measurements recorded since the treatment started.

**7.1.6 Progression-Free Survival**

Progression-free survival (PFS) is defined as the duration of time from start of treatment to time of progression.

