##### **Phase II portion:**

Primary Endpoint: Efficacy of the combination therapy will be determined by the overall response (ORR) rate/proportion with response including complete response rate/proportion as assessed by RECIST 1.1 criteria.

Secondary Endpoints:

Safety will be defined by the frequency of protocol specified therapy-related grade 3-5 adverse events including events of clinical interest for duration of protocol specified therapy and an additional 60 days beyond that, as assessed by NCI's CTCAE version 4.0.

Survival endpoints for efficacy are 24-month Overall Survival (OS) and 24-month Progression-Free Survival (PFS) in subjects treated with the combination by RECIST 1.1 criteria.

To descriptively characterize the circulating immune cell repertoire before and after start of combination therapy with High Dose Interlukin-2 in combination with the immune checkpoint inhibitor Nivolumab

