**6.3 Follow-Up Procedures**

For patients who have stopped all protocol specified therapy (IL2 and nivolumab for up to 48 weeks), follow up will be done every 12 weeks (counting from week 1) via phone or other forms of communication. In these patients, scans and/or labs will be per the treating investigator’s discretion/per standard of care and not dictated by the protocol.

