## 11.2 Data Analyses Plans

Primary Endpoint Analysis:

Phase 1b: DLT count and proportion will be reported. Type, grade and attribution will be described by body system in the first 10 DLT evaluable patients. Number of IL-2 cycles and doses and Nivolumab doses will be summarized.

Phase II: Overall response rate at 12 weeks will be reported with the sample size and proportion of evaluable patients and the corresponding 95% exact binomial confidence interval.

Secondary Endpoint Analyses:

Safety will be defined by frequency of drug-related grade 3-5 adverse events including adverse events of interest within the duration of protocol, specified therapy and an additional 60 days following the last dose with the combination of HD IL2 and nivolumab, as assessed by NCI's CTCAE version 4.0. Counts and frequencies will be reported by body system, type and grade. Cycles and of each drug and doses/cycle of IL-2 will be described using descriptive statistics.

Survival endpoints are 24-month Overall Survival (OS) and 24-month Progression-Free Survival (PFS) as assessed by RECIST 1.1 criteria in subjects treated with the combination. Product-limit estimates from Kaplan-Meier methods will be used to report the 24-month OS and PFS proportions with 95% confidence intervals. Kaplan-Meier figures will be produced.

Interim Analysis for efficacy: An interim analysis for efficacy is planned after 12 response evaluable patients have been enrolled (total in the phase I b/II portions). If 2 or less patients have a response at 12 weeks then the trial will terminate. .

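### PFS is defined as time to progression only: death is not an event and no censoring rule is given, so 24-month PFS is overstated if a patient dies by month 24 without documented progression

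*Combined protocol and SAP*

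**What the plan says.** Section 7.1.6 defines the endpoint in one sentence: "Progression-free survival (PFS) is defined as the duration of time from start of treatment to time of progression".

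Progression is defined in Section 7.1.4 by what happens to lesions. For target lesions it is "At least a 20% increase in the sum of the LD of target lesions" over the smallest recorded sum, or a new lesion. For non-target lesions it is "Appearance of one or more new lesions and/or unequivocal progression of existing non-target lesions". Death is not part of either definition.

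The Study Endpoints section (phase II) makes PFS a secondary efficacy endpoint: "Survival endpoints for efficacy are 24-month Overall Survival (OS) and 24-month Progression-Free Survival (PFS) in subjects treated with the combination by RECIST 1.1 criteria". Section 11.2 gives the estimator: "Product-limit estimates from Kaplan-Meier methods will be used to report the 24-month OS and PFS proportions with 95% confidence intervals". Neither says which events count or when a patient is censored.

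Elsewhere, death ends follow-up (5.7) and is a safety outcome (8.2, 8.3.2), but it is never a PFS event. Loss to follow-up (5.8.7) is a reason to leave the study, with no censoring date attached.

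Two further provisions bear on how often death might come before documented progression. Section 7.1.4.3 has a reporting category for "global deterioration of health status requiring discontinuation of treatment without objective evidence of disease progression at that time", followed by the request that "Every effort should be made to document the objective progression even after discontinuation of treatment". Section 6.3 says that, once all protocol therapy has stopped, scans are at the investigator's "discretion/per standard of care and not dictated by the protocol"; footnote 9 to the Time and Events Table (6.4) says the same.

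**The concern.** PFS is normally read as time to progression or death. This plan gives an explicit definition that stops at progression. An analyst who follows 7.1.6 would treat a patient who dies without documented progression as having had no event. An analyst who follows convention would count the death. The same data could then give two 24-month figures, and nothing in the plan settles the choice before the data are seen.

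The literal reading errs in one direction only, in favour of the regimen, and the 95% confidence interval does not allow for it. At stake is whether a named secondary efficacy endpoint measures what its label says.

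**Working it through.** **No plan figure to reproduce.** The documents state no assumed PFS rate, event count or power for PFS. The only relevant design figure is the 23 evaluable patients in 11.1.

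**Direction.** Suppose a patient who dies without progression is censored at death. With no tied times, the Kaplan-Meier estimates satisfy

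S_PFS(24) = S_TTP(24) × ∏(1 − 1/n_i),

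where TTP is time to progression, the product runs over deaths without progression by month 24, and n_i is the number at risk at each such death. Every factor is below 1. So S_TTP(24) is strictly above S_PFS(24) when at least one such death occurs by month 24 and S_TTP(24) is above zero. Deaths after month 24 do not enter the product.

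**Size, under assumptions.** Inputs: n = 23 (11.1). Assumed, because the documents do not give them: complete follow-up to 24 months; 6 patients alive and progression-free then; 17 first events, of which d = 1, 2 or 3 are deaths without progression.

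- Deaths counted as events: 6/23 = 26.1%.
- Deaths censored, smallest effect (all such deaths come first): 6/(23 − d).
- Deaths censored, largest effect (all such deaths come last): (6 + d)/23.
- The mean is taken over all C(17, d) orderings of the 17 events.

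| d | Lowest | Highest | Mean over orderings | Largest shift |
|---|---|---|---|---|
| 1 | 6/22 = 27.3% | 7/23 = 30.4% | 28.2% | 1/23 = 4.3 points |
| 2 | 6/21 = 28.6% | 8/23 = 34.8% | 30.6% | 2/23 = 8.7 points |
| 3 | 6/20 = 30.0% | 9/23 = 39.1% | 33.1% | 3/23 = 13.0 points |

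For scale, one standard error at 26.1% is √(0.2609 × 0.7391 / 23) = 9.2 points. In this example one or two deaths stay within one standard error, while three can exceed it. That comparison depends on the assumed rate: at 4/23 the standard error is √(0.1739 × 0.8261 / 23) = 7.9 points, and two deaths can shift the figure by 8.7.

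**Cross-check with constant hazards.** Assume a true median PFS of 12 months, so 24-month PFS is 0.5² = 25.0%. If a share f of PFS events are deaths without progression, the figure as written is 0.25^(1 − f): 28.7% for f = 0.10 and 33.0% for f = 0.20.

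**Are such deaths plausible?** Section 1.2 puts IL-2 mortality below 1% in recent trials, so fewer than 23 × 0.01 = 0.23 treatment deaths would be expected. That bound does not cover deaths from disease or other causes before progression is documented, and the deterioration category in 7.1.4.3 shows that the plan foresees patients at risk of this.

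**Does the simple correction create a problem of its own?** It can. Suppose all deaths count but living patients are censored at their last scan. In an assumed extreme case, 11 of 23 progress by week 48 and 12 do not. Of those 12, 10 survive with no later scan and 2 die before month 24.

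- Deaths censored: 12/23 = 52.2%.
- Deaths counted, none of the 10 scanned later: only the 2 who die remain at risk, so 12/23 × 1/2 × 0 = 0%, although 10/23 = 43% are alive without known progression.
- Deaths counted, 5 of the 10 scanned through month 24: 12/23 × 6/7 × 5/6 = 37.3%.

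Where scanning lapses, a bare change of definition can therefore push the estimate too low.

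**The case against.** The strongest reply is that 7.1.6 omits death rather than excluding it. PFS sits beside OS under survival endpoints, Kaplan-Meier is specified, and an analyst might well count deaths from the label alone. This stands in part: a reader might infer that the reported figure will be too favourable, and the documents do not support that prediction. They support the narrower statement that the stated rule, if followed, gives time to progression.

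A reader might also infer that any death without progression distorts the result. It does not: only deaths by month 24 matter, and only while the estimate is above zero.

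A third tempting inference is that every scan after week 48 is discretionary. Footnote 9 says so for patients who have stopped protocol therapy, but footnote 11 covers patients who continue nivolumab past 48 weeks and keeps scheduled scans for them. The flat statement is too strong, and the two footnotes need reconciling. Patients who stop because of progression already have their event and are unaffected.

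Finally, the magnitudes are illustrative: the base rate, the number of deaths and complete follow-up are all assumed, and 23 patients are reached only if stage 1 is passed. PFS also carries no hypothesis or decision, so this could be called a one-line clarification. The limits on magnitude are fair. The low stakes do not remove the point, because the written definition does not match the endpoint's name and correcting it is cheap.

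**Conclusion.** The point holds in this form. The only PFS definition ends at lesion-based progression, and nothing else in the documents makes death an event or supplies a censoring rule. Followed as written, 24-month PFS is time to progression; it is overstated if a patient dies without documented progression by month 24, and is free of bias on this point otherwise.

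Under the assumed 26.1% base rate the overstatement averages 2.2, 4.5 or 7.0 points for one, two or three such deaths (28.2, 30.6 and 33.1 less 26.1), and at most 13.0 points. The true size cannot be derived from the documents.

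It would be wrong to read this as a threat to the trial's conclusion on activity. The response-rate design, the interim rule and the criterion for recommending further study do not use PFS. The change should be made, but it is not critical.

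**What to change.** 1. In 7.1.6, replace the definition with: *PFS is the time from start of treatment to first RECIST 1.1 progression or death from any cause, whichever is first; patients alive without progression are censored at the last adequate tumour assessment.* Refer to it in 11.2.
2. Prespecify how deaths after a long gap in tumour assessment are handled. One option: a death after two or more missed 12-weekly assessments is censored at the last adequate assessment in the main analysis, with a sensitivity analysis that counts all deaths as events. Such a rule leaves some of the upward bias in the main figure, which is why both should be reported.
3. Reconcile footnotes 9 and 11 of the Time and Events Table on scans for patients who continue nivolumab beyond 48 weeks.

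The cost is wording plus one extra sensitivity analysis. Deaths are already collected for OS, so no visits, scans or patients are added and the sample size does not change. The downside is a less favourable PFS figure if such deaths occur.

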## 7.2 Safety/Tolerability

Analyses will be performed for all patients having received at least one dose of study drug. The study will use the CTCAE version 4.0 for reporting of adverse events (<http://ctep.cancer.gov/reporting/ctc.html>).

## 8.0 ADVERSE EVENTS

### 8.1 Experimental Therapy

For the most recent safety update on Contraindications, Special Warnings and Precautions for Use, Interaction with other medications and Adverse Reactions, please refer to the current Investigator's Brochure or package insert.

### 8.2 Adverse Event Reporting Requirements

Adverse event (AE) monitoring and reporting is a routine part of every clinical trial and is done to ensure the safety of subjects enrolled in the studies as well as those who will enroll in future studies using similar agents. Data on adverse events will be collected from the time of initial study treatment administration or intervention through 60 days after the last dose of **study treatment** (study treatment here refers to the two possible cycles of interleukin-2 and/or last dose of nivolumab up to 48 weeks of therapy, whichever is later). Any serious adverse event that occurs more than 60 days after the last study treatment and is considered related to the study treatment must also be reported. Serious Adverse Events (SAEs) will continue to be followed until:

- Resolution or the symptoms or signs that constitute the serious adverse event return to baseline;
- There is satisfactory explanation other than the study treatment or intervention for the changes observed; or
- Death.

The investigator is responsible for the detection, documentation, grading and assignment of attribution of events meeting the criteria and definition of an AE or SAE. The definitions of AEs and SAEs are given below. It is the responsibility of the principal investigator to ensure that all staff involved in the trial is familiar with the content of this section.

Any medical condition or laboratory abnormality with an onset date before initial study treatment administration or intervention is considered to be pre-existing in nature. Any known pre-existing conditions that are ongoing at time of study entry should be considered medical history.

All events meeting the criteria and definition of an AE or SAE, as defined in Section 8.3, occurring from the initial study treatment administration or intervention through 60 days following the last dose of the study treatment (study treatment here refers to the two possible cycles of interleukin-2 and/or last dose of nivolumab up to 48 weeks of therapy whichever is later) or study intervention must be recorded as an adverse event in the patient's source documents and on the CRF regardless of frequency, severity (grade) or assessed relationship to the study treatment or intervention.

In addition to new events, any increase in the frequency or severity (i.e., toxicity grade) of a pre-existing condition that occurs after the patient begins study treatment or intervention is also considered an adverse event.

